We expect that exciting the matrix cell-rich areas of the thalamus, such as the ventral anterior section, will lead to a decrease in criterion (c), indicating a shift of the decision criterion towards a more liberal response bias. Conversely, exciting the core cell-rich areas of the thalamus, like the dorsal posterior section, will increase sensitivity (d'), resulting in improved differentiation ability in stimulus perception. Conversely, we also anticipate that inhibiting the ventral anterior thalamus will have the opposite effect on criterion (c), leading to a more conservative decision bias. Inhibiting the dorsal posterior thalamus will reduce sensitivity (d'), resulting in a decreased ability to differentiate between stimuli. By observing these effects, we aim to unravel the distinct causal roles of the anterior and posterior thalamus in conscious perception. This disentanglement will provide valuable insights into the mechanisms of specific thalamic regions in shaping perceptual processes.

Number of Subjects, Recruitment and Informed Consent

Our study will involve the enrollment of 60 participants, who will be randomly assigned to two groups, with each group consisting of 30 participants. The participants will be divided based on the type of transcranial LIFUP they will receive, either excitation or inhibition, targeting four specific thalamic areas. See experimental design details below. Healthy participants will be recruited by listing on UMClinicalStudies.org and by postings at area colleges and community groups in Ann Arbor. Interested volunteers will call the phone number of a designated recruiter for an initial phone screening. The initial phone screening will consist of questionnaires related to medical history, demographic information, handedness, inclusion and exclusion criteria. If interested, the participant will

complete the questionnaires, which will be reviewed by the study team. Once eligibility is confirmed by the study team, the one-time research study session will be scheduled. Participants may be screened for COVID-19 prior to entry into the hospital per hospital guidelines.

[figure not shown]

Figure 3. Randomized study group assignment. A total of 60 participants will be enrolled in the study and randomly assigned to two groups, each comprising 30 participants. The group assignment will be based on the type of transcranial LIFUP they will receive, either in the form of excitation or inhibition.

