Experimental Design. The experimental will consist of a 10-minute baseline period (LIFUP-OFF) followed by four 10-minute sessions of stimulating (LIFUP-ON) four thalamic areas. The order of thalamic area stimulation will be counterbalanced across participants and will include the ventral anterior (VA), dorsal anterior (DA), ventral posterior (VP), and dorsal posterior (DP) sections of the thalamus. The center coordinates of these thalamic regions will be derived from a previous study on thalamic parcellation ⁴⁰. Given that previous studies have not indicated any functional lateralization of the thalamic areas, we will target only the left hemisphere for the sake of convenience in this study.

Perceptual Task. The quality of conscious perception will be assessed by a well-established psychometric approach, the near-threshold perceptual task ^{41,42}. This task allows one to compare the neural activity evoked by identical weak stimuli that are sometimes perceived and sometimes remain subliminal (**Figure 5**). It thus rules out potential confounds of variability derived from the differences in physical property of the stimuli. All stimuli will be programmed using E-Prime (Psychology Software Tools, Pittsburgh, PA) and delivered via a laptop computer. Stimuli will be presented at the threshold of subjective recognition. An adaptive thresholding procedure will be conducted whereby image contrast will be titrated to reach a 50% subjective recognition rate for each subject. Stimuli will include two common visual object categories: faces and houses. Participants' task is to report the category ("F" or "H") of an image presented and their recognition experience ("Yes" or "No"). Specifically, they will be instructed to report the object category regardless of their recognition experience and, in cases of unrecognized images, to make a genuine guess (two-alternative choice discrimination). Then, they will be instructed to report whether they see an object, such that even if the object appears unclear or noisy, they should respond "yes", but if they see nothing or only low-level features, they should respond "no".

[figure not shown]

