Figure 5. Visual task design. During each 10-min session, participants will complete an image recognition task. Stimuli (faces, houses, and scrambled images) will be presented at the threshold of subjective recognition. Participants' task is to report the category ("F" or "H") of the image presented and their recognition experience ("Yes" or "No").

The stimulus set will include real and scrambled images, the latter will be created by phase-shuffling of a randomly chosen real image from each category to preserve category specific low-level image features^{41,42}. Because scrambled images serve as "catch trials" to determine the subjects' baseline tendency to give positive responses to a question about their recognition experience. The pre-stimulus interval will vary randomly from trial to trial between 2 and 4 seconds to prevent stimulus timing predictability. The stimuli will be presented in a randomized order to prevent category predictability.

Primary Outcome Measure

Perceptual criterion (c) and sensitivity (d') derived from the Signal Detection Theory (SDT) analysis. These measures will be assessed over a timeframe spanning from the baseline to 60 minutes after the LIFUP stimulation.

Data Analysis and Statistics

For each 10-min session, we will calculate sensitivity (d') and criterion (c) using subjective reports of recognition as "yes" or "no". (d') indicates the ability to discriminate between real and scrambled images. It is computed by subtracting the z-transformed False Alarms Rate (FAR) from the z-transformed Hit Rate (HR): $d' = Z(HR) - Z(FAR)$, where Z is an inverse normal cumulative distribution function. (c) reflects the tendency to make "yes" reports to indicate recognition, regardless of whether the stimulus is a real or a scrambled image, which is computed as: $c = -0.5 \times (Z(HR) + Z(FAR))$. We will also calculate percent of correct responses as an operational measure of two alternative-forced-choice sensitivity using subjective category reports, i.e., responses to the first question: "Face" or "House".

We will conduct a repeated-measures ANOVA, considering measurements taken during both the baseline and the four thalamic areas' stimulation sessions. This analysis will be

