performed at the group level to assess the effects of LIFUP on the perceptual measures. To determine statistical significance, we will apply a false discovery rate (FDR) correction and set the threshold at $\alpha < 0.05$. This approach will help us identify any significant differences between the baseline and the different thalamic area stimulations in terms of sensitivity (d') and criterion (c).

Anticipated Results and Interpretation

We expect to observe differential changes in the perceptual outcomes based on the LIFUP stimulation of different thalamic areas. We anticipate that stimulation of the ventral anterior thalamus will decrease criterion (c), indicating a shift of the decision criterion in the liberal direction. During exciting the dorsal posterior thalamus, we expect an increase in sensitivity (d'), reflecting a higher sensitivity in differentiating between stimuli. Conversely, when inhibiting the ventral anterior thalamus and the dorsal posterior thalamus, we expect the opposite effects on criterion (c) and sensitivity (d') compared to the outcomes seen during their respective excitations. The effects of stimulating the dorsal anterior thalamus and the ventral posterior thalamus are expected to lie between the effects of ventral anterior and dorsal posterior thalamic stimulation. These findings should provide valuable insights into the specific contributions of these thalamic regions in shaping conscious experiences.

Power Analysis

We considered a recent review article that summarized 25 LIFUP studies in humans. These studies had sample sizes ranging from 1 to 50, with a median value of 16. Since the neuromodulation effect is dependent on various factors, such as parameter settings and specific brain regions targeted, determining a prior effect size is challenging. However, we have planned a subject number of 30 per group, which exceeds the median sample size reported in the literature. With a larger sample size, we aim to enhance the statistical power, reliability and sensitivity of our findings, enabling us to draw robust conclusions about the neuromodulatory effects of LIFUP on conscious perception.

Biological Variables

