The proposed procedure entails minimal risks, while the potential knowledge gains hold significant importance for humanity. As a result, the risk-to-benefit ratio is very low. These experiments offer a unique opportunity to understand the neuromodulation's impact on human conscious perception. The potential insights gained from this study justify the minimal risks involved, making it a valuable and worthwhile endeavor.

Procedures for Minimizing Risks

All research subjects will undergo a thorough screening process to ensure they meet the inclusion and exclusion criteria. Additionally, if any subjects express or exhibit anxiety related to the LIFUP procedure, they will have the opportunity to discuss their feelings or withdraw from the experiment if they wish.

We are committed to strictly adhering to the FDA limit for diagnostic ultrasound intensity (as outlined in the FDA guidance document on diagnostic ultrasound systems and transducers) during the LIFUP procedure to maintain safety and prevent any adverse effects. The FDA previously determined that the use of LIFUP in our studies carries nonsignificant risk (NSR).

Adverse Events

Adverse events will be monitored throughout the procedures and for 24 hours after the procedure via a phone call to the subjects. We will follow their medical record for 30 days following the procedure. Complications or adverse events that are observed by the investigator or reported by the subject will be recorded. For all adverse events and complications, a description of the event, date first observed, any action taken, and ultimate outcome will be recorded.

For all adverse events, sufficient information will be pursued and/or obtained as to permit 1) an adequate determination of the outcome of the event (i.e., whether the event should be classified as a serious adverse event) and; 2) an assessment of the causal relationship between the adverse event and the investigational device, or if applicable, the other study treatments of diagnostic product(s). Adverse events felt to be associated with the investigational device, or if applicable, other study treatment or diagnostic product(s) will be followed until the event (or its sequelae) or the abnormal test finding resolves or

stabilizes at a level acceptable to the sponsor-investigator. Adverse events will be reported to the IRB according to their reporting guidelines.

Serious and Unanticipated Adverse Device Events

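### The repeated-measures ANOVA needs all five sessions and the plan has no rule for incomplete participants, so by default one missing session discards a person's completed sessions too

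*Combined protocol and SAP*

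**What the plan says.** Under Experimental Design, each participant has a "10-minute baseline period (LIFUP-OFF) followed by four 10-minute sessions of stimulating (LIFUP-ON) four thalamic areas", which makes five within-person measurements. Baseline always comes first; for the areas, "The order of thalamic area stimulation will be counterbalanced across participants". Data Analysis and Statistics then states: "We will conduct a repeated-measures ANOVA, considering measurements taken during both the baseline and the four thalamic areas' stimulation sessions". For significance, "we will apply a false discovery rate (FDR) correction and set the threshold at" 0.05.

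Procedures for Minimizing Risks says of participants who are anxious about the procedure that "they will have the opportunity to discuss their feelings or withdraw from the experiment if they wish".

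On sample size, the section on number of subjects says: "Our study will involve the enrollment of 60 participants, who will be randomly assigned to two groups, with each group consisting of 30 participants". Power Analysis adds that "determining a prior effect size is challenging" and that "we have planned a subject number of 30 per group, which exceeds the median sample size reported in the literature".

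The document does not define an analysis set, a method for missing sessions, a replacement rule, a dropout allowance or a sensitivity analysis.

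**The concern.** A classical repeated-measures ANOVA has no place for a person with an empty cell. The analyst must either delete that person or fill in the value, and the plan authorises neither. Deletion is what normally happens. Someone who stops after the second area has given a usable baseline and two usable area sessions, and all three would be discarded. A session lost to technical failure has the same effect.

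Two things are at stake. Valid data are thrown away in a study whose 30 per group rests on no power calculation. And if leaving is related to how a person responds to stimulation, a completer-only contrast estimates something other than the effect in those randomised. Because the plan is silent, the choice would be made after the data are seen.

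**Working it through.** **1. The plan's own figure.** The 30 per group cannot be reproduced. It was set by comparison with a literature median of 16, with no effect size, SD, power or dropout rate. Every rate and SD below is therefore an assumption.

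**2. Data discarded.** Suppose 3 of 30 stop after three of the five sessions.
- Possible values: 30 × 5 = 150.
- Complete-case: 27 × 5 = 135.
- All completed sessions: 150 − 3 × 2 = 144.
- Valid values lost by deletion: 144 − 135 = 9.

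A standard repeated-measures ANOVA routine given these incomplete data refused to run because they were unbalanced. A mixed model used all 144 values from all 30 people.

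**3. Chance that the gap matters.** The probability that at least one of 60 people is incomplete is 1 − (1 − d)^60. It is 70% at d = 2% and 95% at d = 5%.

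**4. Precision when withdrawal is unrelated to outcome.** Assumed SDs: between persons 0.4, response to stimulation 0.3, session residual 0.3. The person effect cancels in a ventral-anterior-minus-baseline difference, so its variance per person is 0.3² + 2 × 0.3² = 0.27.
- No one missing: 0.27/30 = 0.0090.
- Completers at 10%: 0.27/27 = 0.0100. Completers at 20%: 0.27/24 = 0.01125.
- All-session likelihood estimate: invert the sum over participants of X′V⁻¹X, taken over each person's observed sessions. Withdrawal is equally likely after the first, second or third stimulation session, and response is shared across areas. This gives 0.00924 at 10% and 0.00951 at 20%.
- Averaged over the chance number of withdrawals, the completer variances are 0.01003 and 0.01134. The ratios are 0.01003/0.00924 = 1.09 and 0.01134/0.00951 = 1.19.

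Completers therefore have about 9% and 19% more variance. If responses to the four areas are independent instead of shared, the same calculation gives about 7% and 15%. No method can recover more than the full loss: 30/27 = 1.11 and 30/24 = 1.25.

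**5. Power from the smaller n alone.** One paired contrast, standardised effect 0.5 (assumed), two-sided 0.05 without FDR: 75% at n = 30, 72% at 28, 71% at 27, 65% at 24.

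**6. Bias if leaving is related to response (stress cases).**
- *Leaving depends on the observed fall in c.* The true effect is −0.20, with the SDs of step 4. About 25 completers of 30 give −0.12 to −0.14, and about 22 give −0.07 to −0.10. Likelihood-type estimation on all sessions gives −0.20 to −0.21, and a plain random-intercept model gives −0.18 to −0.21. Missing-at-random holds here by construction.
- *Leaving depends on the person's unobserved response.* The true mean is −0.30, response SD 0.4, residual SD 0.5, about 10.5% leaving. Completers give −0.26. The simple mean over everyone with the session observed gives −0.28. The bias is modest and is only partly removed.

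**7. Which model can replace the ANOVA.** Baseline is always block 1. Over all 24 area orders, an intercept, four condition terms and four categorical block terms make 9 columns of rank 8, and the baseline-versus-area contrasts are not estimable. A linear block term makes them estimable only by extrapolating the trend in blocks 2 to 5 back to block 1. Under the assumed SDs that raises contrast variance by about 42% to 83% even with no withdrawals. Position coded sum-to-zero over the four stimulation blocks, and zero at baseline, gives 8 columns of rank 8 and the contrasts are estimable.

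**The case against.** The strongest reply is that the problem may never arise. The study is a single visit, Compensation ties payment to completing it, and the protocol describes the technique as well tolerated. The withdrawal sentence is an ordinary participant right, not a forecast of attrition. Exclusion of incomplete participants is also inferred from the method and written nowhere. All of this stands. It limits the expected size, but it does not supply the missing rule.

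A reader might infer that those who withdraw will have left in reaction to the stimulation, so that the result describes only people who tolerated all four areas. The documents do not support that. The withdrawal sentence concerns anxiety about the procedure, gives no timing and could apply before any sonication. Nothing links leaving to a shift in c, and missing sessions can have other causes. The 7 of 64 respondents with symptoms, cited in the safety section, is a symptom rate and not a withdrawal rate.

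A reader might also infer that withdrawals would spoil an exact counterbalance. Thirty per group is divisible by neither 4 nor 24, so exact balance of area positions or of full orders within a group was never available.

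**Conclusion.** The point holds as a gap in the analysis plan. The named method needs five values per person, incomplete participants are possible, and nothing prevents complete sessions from being discarded. The effect is nil with no missing sessions. At an assumed 10% to 20% unrelated withdrawal it is about 9% to 19% extra contrast variance, under assumed SDs and a response shared across areas.

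Bias is possible but not shown. It is tempting to read the stress cases in step 6 as a forecast that the ventral anterior effect will be roughly halved. They rest on an assumed link between leaving and response and on losses of roughly 5 to 8 people in 30, for which the documents give no basis. The all-session estimate recovers the truth there largely because the assumed mechanism is missing-at-random. The change is worth making because it is cheap and loses nothing of substance if everyone completes.

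**What to change.** In Data Analysis and Statistics, replace the repeated-measures ANOVA for c and d' with the following.

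- A linear mixed model fitted by REML with Kenward-Roger degrees of freedom, using every completed session of every randomised participant, including those who later withdraw.
- Session condition (baseline, VA, DA, VP, DP) as a fixed effect and participant as a random effect. Fit it within each stimulation group, or add group and group-by-condition terms.
- No block position across all five blocks. If order is adjusted for, code position only among the four stimulation blocks, sum-to-zero and set to zero at baseline.
- The planned baseline-versus-area contrasts, with FDR, unchanged.
- Withdrawals and missing sessions reported by group and block, with reasons.
- The complete-case ANOVA as a sensitivity analysis.

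The cost is a revised paragraph and slightly more analysis work, with no extra participants or procedures. The model relies on missing-at-random, which the plan should state. That assumption is weaker than the complete-case analysis needs, but it corrects the estimate only partly if withdrawal depends on unobserved response.

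### Baseline enters only as a fifth ANOVA level: name contrast-specific error terms, and use baseline as a covariate for excitation versus inhibition

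*Combined protocol and SAP*

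**What the plan says.** Data Analysis and Statistics computes d' and c for each 10-minute session, then plans a repeated-measures ANOVA "considering measurements taken during both the baseline and the four thalamic" sessions. The analysis is "performed at the group level to assess the effects of LIFUP on the perceptual measures", with FDR correction at 0.05, and its purpose is to "identify any significant differences between the baseline and the different thalamic area stimulations" in d' and c. The natural reading is a five-level session factor with LIFUP-OFF as one level.

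The section gives no error term, sphericity check or correction, post-hoc method, group factor, group-by-session term or covariate.

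Experimental Design puts the LIFUP-OFF block first for everyone and counterbalances only the order of the four areas. Under Number of Subjects, Recruitment and Informed Consent, participants are "randomly assigned to two groups, with each group consisting of 30 participants", excitation or inhibition. Anticipated Results and Interpretation predicts opposite effects in the two arms.

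**The concern.** Baseline differs in kind from the other four sessions: it is unstimulated and always first. If people differ in how they respond to being stimulated, the four stimulation sessions share that response and baseline does not. Area-minus-baseline differences would then vary more between people than area-minus-area differences. A single error term pooled over five levels would be too small for the first and too large for the second. The wording leaves this choice open, so an analyst could make it after seeing the data.

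Separately, excitation versus inhibition is the only comparison protected by randomisation between participants. Baseline d' and c are measured before the arms diverge and are already collected, yet the plan does not use them to sharpen that comparison. The sample size rests on no effect size or SD, so precision that costs nothing is worth having.

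**Working it through.** **Inputs from the documents.** Five sessions per participant; 30 per group, 2 × 30 = 60, which agrees with the stated total; threshold 0.05 with FDR. The 30 cannot be rebuilt because no effect size, SD or power is given. Two-sided tests are assumed. All variances and correlations below are assumptions.

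**Step 1: pooled error, correlation form.** Let all sessions have variance 1, area-area correlation ra and baseline-area correlation rb.
- Pooled variance of a difference: 2(1 − 0.6ra − 0.4rb), on 4 × 29 = 116 df.
- True variance: 2(1 − rb) for a baseline-area difference, 2(1 − ra) for an area-area difference.
- Example, ra = 0.7 and rb = 0.5: pooled 2 × 0.38 = 0.76, against a true 1.00 (baseline) and 0.60 (area). The SE ratios are √0.76 = 0.87 and √(0.76/0.60) = 1.13.

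Simulated rejection rates with no true effect (n = 30, 40,000 runs, nominal 5%):

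| ra | rb | baseline-area, pooled | area-area, pooled |
|---|---|---|---|
| 0.6 | 0.6 | 5.0% | 5.0% |
| 0.7 | 0.6 | 7.0% | 3.6% |
| 0.7 | 0.5 | 8.7% | 2.8% |
| 0.8 | 0.5 | 12.0% | 1.5% |
| 0.5 | 0.7 | 2.1% | 7.1% |

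Paired tests with their own SD (29 df) gave 4.8% to 5.0% in every row. The omnibus F test was only mildly affected: 5.3% to 6.8% over the second to fourth rows.

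**Step 2: the same in person-by-stimulation form.** Let session error variance be 1 and let the stimulation sessions share a person-specific response with SD tau.
- Pooled mean square: 1 + 0.2tau², which is 1.05, 1.20, 1.45 and 1.80 at tau = 0.5, 1, 1.5 and 2.
- Pooled variance of a difference: 2 + 0.4tau². True variance: 2 + tau² (baseline-area) and 2 (area-area).
- At tau = 2 the baseline SE ratio is √(3.6/6) = 0.77.
- Simulated baseline-contrast rates: about 6%, 8%, 10% and 13%. Area contrasts fall from about 4.4% to 0.9%.
- With Benjamini-Hochberg over the four baseline contrasts (family size assumed), the chance of any false positive is roughly 8% to 13% at tau = 1 to 2 on pooled error, against about 4% with paired errors.

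**Step 3: baseline as covariate for excitation versus inhibition, one area.**
- Equal variances, correlation r: change-score variance 2(1 − r), ANCOVA variance 1 − r², ratio (1 + r)/2. This is 0.75, 0.85 and 0.90 at r = 0.5, 0.7 and 0.8. For an assumed difference of 0.5 SD with 30 per arm (normal approximation), power goes from 49% to 61%, 71% to 77% and 87% to 90%.
- Allowing for tau, with person variance 1 and error variance 1: change-score variance 2 + tau², ANCOVA variance tau² + 1.5. The ratios are 1.5/2 = 0.75, 2.5/3 = 0.83 and 5.5/6 = 0.92 at tau = 0, 1 and 2.
- The saving is therefore about 25% down to 8%, smallest where the pooled-error problem of step 2 is largest.

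**Step 4: what error terms cannot repair.** Baseline is always first, so practice or fatigue is mixed with stimulation. An assumed drift of 0.2 SD gives paired baseline-area tests about 18% (r = 0.5) to 28% (r = 0.7) false positives in the direction of the drift, at n = 30.

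**The case against.** The strongest reply is that the plan commits to none of this. It does not say contrasts will use a pooled error, and paired follow-up tests fit its wording equally well and hold their level. A reader might infer that the ANOVA as planned gives wrong error bars. The documents do not support that: it needs both a pooled error and unequal variances or correlations, and they state neither. This part of the reply stands, and it limits the point to leaving the choice open.

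A reader might also infer that baseline should not be an outcome level. That fails too. The stated target is baseline versus each area, no sham is described, and LIFUP-OFF is the only unstimulated comparator. Baseline has to be an outcome for those contrasts.

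Nor is every excitation-versus-inhibition comparison from such a model a change-from-baseline comparison. Group-by-area contrasts among the four stimulation sessions do not involve baseline. A participant-level covariate with a common slope cancels out of within-person area contrasts and does nothing for them.

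Finally, no excitation-versus-inhibition test is written at all, so no change-score test is actually planned. That is correct, and it makes the missing group analysis the first thing to supply. The covariate is then an inexpensive part of writing it.

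**Conclusion.** The point holds as a free improvement. The plan uses the fixed-first baseline only as a fifth repeated level, fixes no error term or sphericity handling, and plans no baseline-adjusted analysis of the randomised comparison.

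The size is conditional. With pooled error and area-area correlation above baseline-area correlation, baseline contrasts run at about 6% to 13% before FDR and area contrasts are conservative. Equal variances and correlations give 5.0%; the reverse pattern puts the excess on the area contrasts. The covariate saves roughly 8% to 25% of the variance of a single-area group difference against change scores.

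It is tempting to quote the 13% and the 25% together. They come from opposite ends of the same assumption: at tau = 2 the saving is about 8%, and the 25% needs tau = 0. The larger threat to the baseline contrasts is the time confounding in step 4 of the working, which this change does not cure.

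**What to change.** Rewrite the analysis paragraph in Data Analysis and Statistics.

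1. **Randomised comparison.** Compare excitation with inhibition on the four stimulation sessions, with group and group-by-area terms. Use each participant's baseline value of the same measure (d' or c) as covariate. Say that the covariate sharpens group differences but leaves within-person area contrasts unchanged.
2. **Baseline-versus-area contrasts.** Keep them. Test each as a paired difference with its own SD (29 df per arm), or in a mixed model with unstructured covariance over the five sessions.
3. **Area-versus-area contrasts.** Use the four-session error or paired differences.
4. **Limitation.** State that these error terms do not remove the time confounding from a baseline that always comes first.

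The cost is one paragraph of analysis text, with no new data, sessions or participants.
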